10.2 Adverse Events

Per the protocol, participants were asked to report any adverse events from initiation of treatment through 24 weeks follow-up. All adverse events will be collected on an adverse event log and coded using MedDRA.

Adverse events will be listed and summarized by MedDRA system organ class and preferred term. Summaries will be of the number of events and number of individuals experiencing events by treatment group and will be created for all adverse events, by severity, and by relationship to treatment. Any events starting outside of the reportable time frame will be included in separate listings and will be excluded from summary tables. If a complete onset date is unknown and it cannot be confirmed that the event occurred during this time period, then the event will be considered a treatment-emergent adverse event.

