### 7.3.4 FINAL STUDY VISIT

Data to be gathered at the final study visit (EOS, end of the 4 weeks post-treatment observation period) is listed in the Schedule of Events table (Section 7.3.7). This visit may also be conducted remotely according to site PI's discretion. In addition, the following will be addressed.

- Record final adverse events as reported by participant or observed by investigator.
- Provide final instructions and/or follow up information to participant.

- Obtain final biorepository sample (if visit is in-person)

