### 7.3.5 DISCONTINUATION OF STUDY MEDICATION

Study medication may be stopped by the study PI due to toxicity concerns or a subject may elect to stop study medication due to personal reasons. For temporary study drug discontinuations, study drug should be restarted after toxicity/safety concerns are resolved. In case of permanent study drug discontinuation, subjects should complete the visit associated with their current treatment cycle and then complete the EOS visit 4 weeks later (e.g. if a subject permanently stops study drug in the middle of their second treatment cycle, they will complete the end of treatment cycle visit 2 (C2) followed by an EOS visit 4 weeks later) (Figure 3). Subjects who do not agree to complete the 4 week post-treatment follow-up must be discontinued due to withdrawn consent and the Early Termination visit should be completed per Section 7.3.6 in place of the current treatment cycle visit.

	Cycle 1	Cycle 2	Cycle 3	Cycle 4	Cycle 5	Cycle 6	EOS	Comments
No Stopping	Green	Green	Green	Green	Green	Green	Green	
Stop during C1	Red	Grey	Grey	Grey	Grey	Grey	Green	Complete C1 and EOS visit 4 weeks later
Stop during C2	Green	Red	Grey	Grey	Grey	Grey	Green	Complete C2 and EOS visit 4 weeks later
Stop during C3	Green	Green	Red	Grey	Grey	Grey	Green	Complete C3 and EOS visit 4 weeks later
Stop during C4	Green	Green	Green	Red	Grey	Grey	Green	Complete C4 and EOS visit 4 weeks later
Stop during C5	Green	Green	Green	Green	Red	Grey	Green	Complete C5 and EOS visit 4 weeks later
Stop during C6	Green	Green	Green	Green	Green	Red	Green	Complete C6 and EOS visit 4 weeks later

**Figure 3. Follow-up visit schedule after permanent study drug discontinuation.** Dark Green: completed visits; Red: stop study medication mid-cycle.

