### 8.3 TIME PERIOD AND FREQUENCY FOR EVENT ASSESSMENT AND FOLLOW-UP

The occurrence of an AE or SAE may come to the attention of study personnel during study visits and interviews of a study participant presenting for medical care, or upon review by a study monitor. All AEs including local and systemic reactions will be captured on the appropriate CRF. Information to be collected includes event description, time of onset, clinician's assessment of severity, relationship to study product (assessed by the site PI or his/her designee), and time of resolution/stabilization of the event and any additional medical treatment employed in its management (assessed by the site PI or his/her designee). All AEs occurring while on study must be documented appropriately regardless of relationship. All AEs will be followed to adequate resolution.

Any medical condition that is present at the time that the participant is screened will be considered as baseline and not reported as an AE. However, if the study participant's condition deteriorates at any time during the study, it will be recorded as an AE. UPs will be recorded in the data collection system throughout the study.

If there are changes to severity of an AE during a single episode, the maximum severity experienced for that episode should be recorded. AEs characterized as intermittent require documentation of onset and duration of each episode.

The study site will record all adverse events with start dates occurring any time after informed consent is obtained until 7 (for non-serious AEs) or 30 days (for SAEs) after the last day of study drug. At each study visit, the investigator will inquire about the occurrence of AE/SAEs since the last visit. Events will be followed for outcome information until resolution or stabilization.

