10.3 Deaths and Serious Adverse Events

A serious adverse event (SAE) is any event that is life threatening, results in death, causes or prolongs hospitalization, leads to a disability or birth defect, or requires an intervention to prevent a disability. SAEs will be listed, and SAEs and treatment-related SAEs will be summarized in the manner mentioned in Section 10.2 if there are enough events to summarize. Deaths will be listed.

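### SAP 10.2 credits the protocol with an adverse event window that protocol 8.3 does not contain, and its undefined reportable time frame may keep late events out of the summary tables

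*SAP*

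**What the plan says.** SAP 10.2 presents its window as the protocol's: "participants were asked to report any adverse events from initiation of treatment through 24 weeks follow-up". Two rules follow from it. The first is "Any events starting outside of the reportable time frame will be included in separate listings and will be excluded from summary tables". The second concerns events with an incomplete onset date: if "it cannot be confirmed that the event occurred during this time period, then the event will be considered a treatment-emergent adverse event". SAP 10.3 carries the approach over to serious events: "SAEs and treatment-related SAEs will be summarized in the manner mentioned in Section 10.2 if there are enough events to summarize". It also says that serious adverse events and deaths are listed.

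Protocol 8.3 tells sites to "record all adverse events with start dates occurring any time after informed consent is obtained until 7 (for non-serious AEs) or 30 days", the 30 days being for serious events and both limits running from the last day of study drug. It adds: "At each study visit, the investigator will inquire about the occurrence of AE/SAEs since the last visit". The final visit, nominally week 28, is one of those visits; protocol 7.3.4 has sites "Record final adverse events as reported by participant or observed by investigator", and the schedules of events in both documents tick adverse events there.

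SAP section 12 states that nothing specified in the protocol was changed.

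**The concern.** I find no place in the protocol that gives the window which the SAP attributes to it. The two windows differ at the start (first dose against consent) and at the end (a fixed 24 weeks against a limit tied to last dose, with a longer limit for serious events).

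This is more than a citation slip, because SAP 10.2 uses a window to decide which events enter the summary tables. If that window is the 24-week one, events that the protocol requires sites to record after week 24 would appear only in listings. Serious events are the most exposed, since their protocol limit is 30 days. Protocol 8.1 treats venous and arterial thromboembolism as serious, so these events carry that longer limit. Safety and tolerability is the first secondary objective, and the tables are what most readers will use to judge it. SAP 9.2 (adverse events of interest) and SAP 10.1 (between-group tests and incidence density) state no event window, so it is unclear which one they would follow.

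**Working it through.** The plan gives no figure to reproduce. The check sets the two windows side by side and counts days.

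**Inputs**
- First dose is day 1. Treatment is six 28-day cycles, so 24 weeks = 6 × 28 = 168 days (protocol 6.1.7 to 6.1.9 and the study design section).
- L is the day of last dose. The protocol 8.3 limits are L + 7 (non-serious) and L + 30 (serious).
- The next cycle may start up to 5 days after the previous one ends (protocol 6.1.5 and the schedule of events). There are five transitions.
- Assumption: the SAP's 24 weeks is read as a cut-off at day 168.

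**Which period the term points to.** SAP 10.2 does not define the reportable time frame. The sentence after the exclusion rule speaks of this time period, and the only period in the section is the 24-week one. That makes 24 weeks the natural reading.

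**Days recordable under 8.3 but after day 168**

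Serious: max(0, L + 30 − 168). Non-serious: max(0, L + 7 − 168).

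| Case | L | Serious | Non-serious |
|---|---|---|---|
| Completer, no gaps | 168 | 198 − 168 = 30 (days 169–198), 30/198 = 15% | 175 − 168 = 7 (days 169–175), 7/175 = 4% |
| Completer, maximum gaps | 168 + 5 × 5 = 193 | 223 − 168 = 55 | 200 − 168 = 32 |

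In the second row, days 169 to 193 lie within the treatment period itself, so a strict day-168 cut-off could drop on-treatment events as well. This is an upper bound; the documents do not report the gaps that occurred.

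**Early stoppers.** The 24-week window is nominally the longer one when L + 7 < 168 (L below 161, non-serious) or L + 30 < 168 (L below 138, serious). After a permanent stop, "subjects should complete the visit associated with their current treatment cycle and then complete the EOS visit 4 weeks later". For illustration, a stop on day 42 with no gaps gives protocol limits of day 49 and day 72. The cycle 2 visit is due on day 56 and the final visit on day 84. That leaves 84 − 49 = 35 non-serious days and 84 − 72 = 12 serious days beyond the protocol limits but inside the SAP window. Events there could be tabulated only if sites recorded them. The visit days also shift with cycle gaps, and do not describe the 20 participants who, according to SAP 3.2.4, completed a 12-week follow-up.

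**Start of the window.** Protocol: consent. SAP: first dose. A treatment-emergent start is a normal choice for tables, but here it is presented as the protocol's own.

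**The case against.** The strongest reply is that the first sentence of SAP 10.2 describes what participants were asked to report and does not define a table. The reportable time frame could then mean the recording window in protocol 8.3. If so, the tables match the protocol's end limits and only the attribution is wrong. This reading is possible, though the back-reference in the next sentence and the absence of any other period in 10.2 count against it. Even then, the sentence misstates the protocol, and a programmer would have two windows to choose from.

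A second reply reads the phrase as 24 weeks of follow-up after treatment, to about day 336 (168 + 168). No event recordable after last dose under 8.3 would then be dropped. That still does not match 8.3.

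A third reply is that nothing is lost from reporting. This is correct: out-of-window events go to separate listings, and serious events and deaths are listed in any case. A reader might infer that serious events after week 24 would go unreported. The documents do not support that; what is at stake is the tables.

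For early stoppers, a reader might infer that the tables would certainly include off-drug events beyond the protocol limits. The documents do not establish this either. Protocol 8.3 limits recording to 7 or 30 days after last dose, but also requires every adverse event arising while on study to be documented, and it asks about events at each visit. The most that can be said is that such events could be tabulated if recorded.

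**Conclusion.** The mismatch is certain: SAP 10.2 attributes to the protocol a window that protocol 8.3 does not contain, leaves the reportable time frame undefined, and declares no departure in section 12. The effect on the tables is conditional. It follows on the natural reading, with 24 weeks taken as day 168.

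On that reading, a completer without cycle gaps has 30 serious-event days and 7 non-serious days that count under the protocol but not in the 10.2 tables or in any 10.3 summary of serious events. The maximum allowed gaps raise the serious figure to 55 days, 25 of them within the treatment period. For early stoppers the difference runs the other way, nominally. All of these are calendar days. The documents give no post-drug event rate, so the number of events affected cannot be estimated. The primary efficacy analysis is not touched. This should be corrected, because the safety tables ought to rest on one stated window.

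**What to change.** Replace the 24-week sentence in SAP 10.2 with one explicit definition of the reportable time frame for summary tables: onset from first dose to last dose + 7 days for non-serious events, and to last dose + 30 days for serious events. These are the end limits of protocol 8.3. State that the treatment-emergent start is narrower than the protocol's start at consent, and declare this in SAP section 12. List events outside the window separately. State that the same window governs the adverse events of interest in SAP 9.2 and the comparisons in SAP 10.1.

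The cost is a few sentences and one date rule in the adverse event dataset. No new visit is needed: the final visit, nominally at day 196 to 203 (28 × 7 = 196, plus 0 to 7 days), falls close to the day-198 limit for a last dose on day 168. The downside should be disclosed: any events recorded for early stoppers after the 7- or 30-day limits would appear only in listings, although some of them fall within 24 weeks of first dose.

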10.3 Deaths and Serious Adverse Events

A serious adverse event (SAE) is any event that is life threatening, results in death, causes or prolongs hospitalization, leads to a disability or birth defect, or requires an intervention to prevent a disability. SAEs will be listed, and SAEs and treatment-related SAEs will be summarized in the manner mentioned in Section 10.2 if there are enough events to summarize. Deaths will be listed.

10.4 Laboratory Evaluations

Laboratory exams (include blood chemistry and hematology) will be collected from each patient and will be summarized by study visit. Box and whisker plots will be generated to show the changes across study visits for key safety labs. These have been produced for the DSMB reports.

If applicable, linear mixed effect models will be constructed modeling change from baseline for key safety lab values over time with study time treated categorically and will be used to compare any post-baseline measures to baseline. Change from baseline will be assessed for substantial violations of normality and if so, a transformation will be considered.

Incidence of treatment-emergent abnormal safety labs at any post-baseline timepoint for all collected lab parameters will be tabulated (similar to that produced for the DSMB reports but DSMB was not focused on treatment-emergent labs), and treatment groups will be compared with chi-squared or Fisher's exact test, if applicable. Treatment-emergent abnormal is defined as a lab value post-baseline that is outside the normal range during the treatment period but is within the normal range at baseline (or at screening, if the baseline value is missing).

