3.2.3 Other Secondary Outcomes

1. Change in PROMIS® Emotional Distress-Depression Short Form (V1.0) T-score from baseline (randomization visit) to weeks 12 and 24 (key timepoint), and the 4-week post-treatment follow-up visit in the pomalidomide and placebo groups.
2. Change in PROMIS® Fatigue Short Form (V1.0) T-score from baseline (randomization visit) to weeks 12 and 24 (key timepoint), and the 4-week post-treatment follow-up visit in the pomalidomide and placebo groups.
3. Proportion of patients requiring no red blood cell transfusion or parenteral iron infusion during the 24-week treatment period in the pomalidomide and placebo groups.
4. Change in the ESS from baseline to that recorded at each individual patient assessment, including the 4-week post-treatment follow-up visit.
5. Change in the ESS from baseline to the average of the week 16, 20 and 24 assessments.
6. Proportion of patients requiring endoscopic interventions for management of bleeding during the 24-week treatment period in the pomalidomide and placebo groups.
7. Incidence and severity of adverse events in the pomalidomide and placebo groups including but not limited to:
 - Venous thromboembolism
 - Arterial thromboembolism
 - Thrombocytopenia
 - Neutropenia
 - Peripheral neuropathy
 - Fatigue
 - Constipation/diarrhea
 - Rash

- Any other AEs or SAEs of at least moderate severity that are possibly related to pomalidomide and deemed medically relevant at masked data review.

8. Change in iron/hemoglobin-related studies including iron saturation, ferritin, hemoglobin, hematocrit, MCV, and MCHC.

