9.4 Secondary Analysis Methods

Unless otherwise specified, changes from baseline in continuous secondary outcomes will be compared between treatment groups using an MMRM model as specified for the primary outcome and analogous generalized linear models will be used for any repeated dichotomous outcomes.

A Hochberg multiple comparison adjustment will be applied to the 5 key secondary endpoints to maintain the overall Type 1 error rate. Treatment groups will be compared for the secondary endpoints as described in Section 7.7.

Treatment groups will be compared for the total amount of packed red blood cell transfusions (units) and iron (mg) infused during the 24-week treatment period (calculated as average over a 4-week period), using an analysis of covariance or rank analysis of covariance if not normally distributed, with adjustment for the measure in the 6 months prior to the screening period and pooled clinical site. If packed red blood cell transfusions are rare, then we will switch to a zero-inflated Poisson regression model or logistic regression, depending on the distribution.

Blinded data review prior to database lock determined the number of RBC transfusions is rare and so RBC transfusions during the 24-week treatment period will be analyzed as yes/no using logistic regression with adjustment for transfusion in the 6 months prior to screening (yes/no) and pooled site.

The blinded data review also indicated the amount of iron infused during the 24-week treatment period is not normally distributed and will be analyzed with rank analysis of covariance (Stokes, Davis and Koch 2000). The rank ANCOVA is completed in 3 steps, (A) ranking the outcome variable and the baseline value separately within each pooled site, (B) obtaining the residuals from a regression of the ranked outcome variable on the ranked baseline variable, separately for each pooled site, and then (C) comparing the treatment groups for the residuals using a Mantel-Haenszel mean score test stratified by pooled site.

Sample SAS code for the rank ANCOVA is as follows:

```
proc rank nplus1 ties=mean out=ranks;
  by sitenum;
  var [outcome variable] [baseline variable]
run;

proc reg data=ranks;
  by sitenum;
  model [outcome ranked variable] = [baseline ranked variable];
  output out=redidual r=resid;
run;

proc freq data=redidual noprint;
  tables sitenum*trtgp*resid / cmh ;
run;
```

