10 SAFETY ANALYSES

10.1 Overview of Safety Analysis Methods

All safety analyses will be performed using all participants in the safety population, regardless of eligibility. The frequency of toxicities potentially attributable to pomalidomide treatment will be determined (e.g., venous/arterial thromboembolism, thrombocytopenia, fatigue, constipation/diarrhea, rash). Treatment and resolution of all safety endpoints will also be documented. Treatment groups will be compared for incidence of events with a chi-squared or Fisher's exact test, and incidence density (events per person-months of exposure) will be calculated for toxicities in the pomalidomide group. Adverse event incidence rates will be included in semi-annual safety reports to the DSMB and annually to the FDA.

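### The safety-laboratory mixed models in SAP 10.4 state a comparison with baseline and name no treatment term, so mean change in several safety labs has no specified between-arm comparison

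*SAP*

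**What the plan says.** SAP 10.4 sets out three things for laboratory data.

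- **Summaries.** Chemistry and hematology "will be collected from each patient and will be summarized by study visit", with box plots for key safety labs.
- **Models.** "If applicable, linear mixed effect models will be constructed modeling change from baseline for key safety lab values over time with study time treated categorically". Their one stated purpose is that they "will be used to compare any post-baseline measures to baseline". The section does not say whether the arms are pooled or fitted separately.
- **Abnormality test.** For treatment-emergent abnormal values, across all collected parameters, "treatment groups will be compared with chi-squared or Fisher's exact test, if applicable". A value counts only if the same parameter was in range at baseline, or at screening when baseline is missing.

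Elsewhere, SAP 10.1 says of toxicities: "Treatment groups will be compared for incidence of events with a chi-squared or Fisher's exact test". SAP 3.2.3 lists as a secondary outcome "Change in iron/hemoglobin-related studies including iron saturation, ferritin, hemoglobin, hematocrit, MCV, and MCHC", and SAP 9.4 states that "changes from baseline in continuous secondary outcomes will be compared between treatment groups using an MMRM model as specified for the primary outcome". The primary model in SAP 9.3 names treatment, visit and their interaction, and supplies code.

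**The concern.** The trial has a randomised placebo arm, and safety is the first secondary objective. Protocol 6.1.8.3 names hematologic toxicity as the main toxicity of the drug. Protocol 8.1 says that toxicity estimates from myeloma probably do not carry over to this population. Placebo is therefore the natural reference for laboratory change, and a contrast against baseline does not use it.

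Laboratory values can move in both arms for reasons unrelated to the drug, such as time trends, variable bleeding and local laboratory methods. A visit-versus-baseline test picks up any such movement. If the arms are fitted separately, the pomalidomide result mixes drug effect with background. If they are pooled, background stays in and the drug effect is diluted. Neither gives the quantity a safety reader wants, which is how much more the value changed on pomalidomide than on placebo.

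**Working it through.** The plan states no alpha, power or effect size for these models, so there is no figure to reproduce. The check is textual, followed by an illustration on assumed shifts.

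**1. Which laboratory comparisons use the randomised arms?**

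| Analysis | Compares arms? | Scale and coverage |
|---|---|---|
| SAP 10.4 mixed models | Not stated; contrast is with baseline | Continuous, key safety labs |
| SAP 10.4 treatment-emergent abnormality | Yes, conditionally | In or out of range, all parameters |
| SAP 10.1 toxicity incidence | Yes | Reported events |
| SAP 9.2 worst platelet and neutrophil categories | No test named | Lowest post-baseline value, baseline ignored |
| SAP 9.4 repeated-measures model | Yes | Continuous: iron saturation, ferritin, hemoglobin, hematocrit, MCV, MCHC |

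Continuous safety labs outside those six (platelets, ANC, WBC, ALT/AST, bilirubin, creatinine) have no specified between-arm comparison of mean change.

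**2. What does the abnormality test leave out?** It cannot see a shift that stays within range. It also cannot count a patient out of range at baseline. SAP 4.2 admits platelets from 100 x10^9/L, while SAP 9.2 takes 150 as the lower normal bound. If that bound is used, a patient with a baseline of 100 to 149 cannot become treatment-emergent abnormal, however far the count falls. Eligibility likewise allows bilirubin up to 2.0, transaminases up to 3 times normal and creatinine up to 2.0 mg/dl.

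**3. Illustration: test against baseline when the drug has no effect.**

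Inputs: 106 and 53 patients (Protocol 10.5) and two-sided tests (SAP 7.1). Assumed: 0.05 per test, one visit, no missing data, and a shift of d SDs of change common to both arms. With m patients,

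P(significant) = 1 − Φ(1.96 − d√m) + Φ(−1.96 − d√m)

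For d = 0.2 and m = 106, d√m = 2.06, which gives 54%.

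| Shared shift (SD) | Pomalidomide arm, m = 106 | Arms pooled, m = 159 | Between-arm contrast |
|---|---|---|---|
| 0.1 | 18% | 24% | 5% |
| 0.2 | 54% | 71% | 5% |
| 0.3 | 87% | 97% | 5% |
| 0.5 | >99% | >99% | 5% |

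**4. The same in platelet units.** Assume a fall of 15 x10^9/L in both arms and an SD of change of 50 (so d = 0.3). Assume also 97 and 48 patients, a 2:1 split of the 145 in the SAP 7.6 site list (24 + 51 + 21 + 16 + 12 + 21).

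- Pomalidomide: 15 / (50/√97) = 2.95, p = 0.003.
- Placebo: 15 / (50/√48) = 2.08, p about 0.04.
- Between arms: expected difference 0, SE = 50 × √(1/97 + 1/48) = 8.8.

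**5. If the arms are pooled.** A true drug effect D appears as (106 × D + 53 × 0)/159 = 0.67 D, plus any shared shift.

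**6. What can the between-arm contrast detect?** At 80% power, (1.960 + 0.842) × √(1/106 + 1/53) = 0.47 SD. Smaller effects could be missed, so the estimate and its interval matter more than the p-value.

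**The case against.** A reader might infer that laboratory changes shared by both arms will be reported as drug effects, or that the plan makes no randomised comparison of laboratory safety. The documents support neither. No section says how a change from baseline will be interpreted. SAP 10.4 plans a between-arm test of abnormal values in the paragraph after the models. SAP 10.1 compares toxicity incidence, including thrombocytopenia, and SAP 7.4 gives the DSMB Fisher's exact comparisons of safety outcomes. These points stand.

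It can also be said that the sentence is an outline which names no covariates or covariance structure either, so silence on treatment is not exclusion. That is fair as far as it goes: the model might be fitted with a treatment term. But the section does state which contrast the model is for, and that contrast is with baseline, so following the text does not produce the randomised comparison.

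Iron repletion and transfusion are the most obvious sources of shared drift, and they act mainly on the six labs that SAP 9.4 already compares between arms. This also stands. For the remaining labs the argument rests on more general sources of drift, and no document gives their size.

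Finally, the models are conditional, Protocol 10.4.4 does not call for them, and no primary or key secondary result depends on them. This limits the importance of the point without removing it.

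**Conclusion.** The point holds as a specification gap of minor weight. The safety-lab models state only a comparison with baseline and name no treatment or treatment-by-visit term, so they cannot isolate a drug effect. For platelets, ANC, WBC, transaminases, bilirubin and creatinine, no other planned analysis compares mean change between arms. The abnormality and toxicity tests cover part of this ground, but not within-range shifts or worsening in patients already abnormal at baseline.

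The textual finding needs no assumptions beyond reading the sections together. The size does: the shared shifts of 0.1 to 0.5 SD, the platelet fall of 15 and SD of 50, the 0.05 level and the absence of missing data are all assumed. They show how a baseline contrast behaves, not that such drift is expected in this trial. The primary endpoint, the key secondary endpoints and the stopping rules are unaffected.

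**What to change.** In SAP 10.4, state that where these models are fitted they take the form: change = baseline value + treatment + visit + treatment x visit, with pooled site added, as in the efficacy models, if numbers allow. Report the pomalidomide minus placebo difference with its 95% CI at each treatment visit. Keep within-arm change from baseline as description only, without tests. The between-arm test of treatment-emergent abnormal values stays as planned beside it.

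The cost is a sentence or two of SAP wording and a few extra terms in a model already planned. No new data are needed, and Protocol 10.4.4 need not change. The edit is best made before treatment assignments are unmasked.
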